Patients will be assessed for disease response at the completion of 4 cycles of treatment. If there has been no response to therapy (i.e. stable disease per IWG-2006), or if disease progression is identified, patients will be eligible to continue on the study with the addition of 5-azacitadine or decitabine, with continuation of Pacritinib, in **Part 2** (Pacritinib + HMA). Patients responding to therapy will continue on Pacritinib monotherapy. Patients with disease progression prior to 4 cycles of Pacritinib are also eligible to initiate the Pacritinib + HMA study portion prior to the completion of 4 cycles. In these patients, disease assessment including bone marrow aspiration should be performed prior to the initiation of Part 2. Patients receiving Pacritinib + HMA will be re-assessed for disease response after 4 cycles of *combination* treatment on Part 2. Patients on pacritinib monotherapy in Part 1 who manifest disease progression at any time, including before or after completion of 4 cycles of treatment, can continue on study in Part 2 with the addition of a hypomethylating agent.

The addition of HMA should be initiated on Day 1 of the next Pacritinib treatment cycle whenever possible. HMA dosing and dosing adjustments should be performed according to the approved package insert, or at a dose of decitabine 20mg/m² IV over 1 hour for 5 days every 4 weeks and according to standard of care (see Section 5.0 for rules of dose reduction or delay).

Duration of Therapy

All patients must complete a screening visit, day 1 visits for each new cycle (+/- 5 days), end of treatment visit and whenever possible, an end of study safety visit 28 days after the last dose of Pacritinib (+/- 7 days).

Patients may remain on study for up to 12 months if the patient demonstrates clinical benefit and no excessive toxicity (i.e. no clinically significant study-drug related grade ≥ 3 toxicity). Patients who are experiencing clinical benefit beyond 12 months and have not experienced excessive toxicity may be eligible to continue therapy after discussion with the PI and the discussion documented in the patient's medical record. After the end of therapy and/or 30 days after your last dose of study drug, the study staff will follow your health status by phone call every 2 months (+/- 2 months) until you receive another cancer treatment.

Treatment is expected to continue until one of the following criteria applies:

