All patients who received any dose of the study agent will be included in the analysis for efficacy and safety. Demographic/clinical characteristics (i.e. including duration of response) and safety data of the patients will be summarized using descriptive statistics such as mean, standard deviation, median and range. For the primary efficacy analysis, we will estimate the ORR for the Pacritinib and Pacritinib + HMA, along with the 95% confidence interval. Patients who drop out of the study before completing all the cycles will be treated as “failures” for the primary analysis. Overall response rate (ORR) during the study period will also be presented with the 95% confidence interval. The association between ORR and patient’s clinical characteristics will be examined by Wilcoxon’s rank sum test or Fisher’s exact test, as appropriate. Toxicity type, severity and attribution will be summarized for each patient using frequency tables. The distribution of time-to-event endpoints (EFS and OS) including overall survival and event free survival will be estimated using the method of Kaplan and Meier. Comparisons of time-to-event endpoints by important subgroups will be made using the log-rank tests. The additional treatment in part 2 will be included in time-to-event analysis as time-dependent covariates.

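### Duration of response is assigned to ordinary descriptive statistics with no censoring rule, so its mean, and usually its median, will be too short if any responses are ongoing at analysis

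*Combined protocol and SAP*

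**What the plan says.** In Section 12.0, under Statistical Analysis Plan, duration of response appears in a parenthesis within the sentence on patient characteristics and safety: "i.e. including duration of response) and safety data of the patients will be summarized using descriptive statistics such as mean, standard deviation, median". The statistics named are mean, standard deviation, median and range.

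Later in the same paragraph a censored method is given to other endpoints: "EFS and OS) including overall survival and event free survival will be estimated using the method of Kaplan and Meier". Duration of response is not among them. The documents give no start date, end event or censoring rule for it. Section 10.0 does define relapse after CR or PR (Table 9) and progression or relapse after hematologic improvement (Table 10).

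Section 4.0 governs how long a response can be watched. "Patients responding to therapy will continue on Pacritinib monotherapy". "Patients may remain on study for up to 12 months if the patient demonstrates clinical benefit", with continuation beyond 12 months possible after discussion with the principal investigator. After therapy, "the study staff will follow your health status by phone call every 2 months" until another cancer treatment starts.

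**The concern.** Duration of response is a right-censored time. A patient still responding at the last assessment has a duration known only to exceed what was observed. Mean, standard deviation, median and range have no place for that information, so the analyst must either enter the ongoing response as if it had ended or leave it out. Both choices shorten the answer, and the shortfall in the mean grows with the true duration of response. The reported figure then reflects length of follow-up as much as the drug.

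At stake is how the durability of any responses is described. No go/no-go rule depends on it.

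**Working it through.** The documents state no figure for duration of response, so there is nothing to reproduce. The check covers direction first, then size under stated assumptions.

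**Inputs from the documents**
- Maximum 40 evaluable patients; target ORR 15% in Part 1 and 30% in Part 2 (Section 12.0). Expected responders: 0.15 × 40 = 6 in Part 1. In Part 2, at most 0.30 × 40 = 12, and only if all 40 entered it.
- Response is assessed after 1 to 4 cycles of 28 days, and nominal time on study is 12 months (Section 4.0). Observation after onset within that period is about 12 − 4 = 8 to 12 − 1 = 11 months.

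**Assumptions (not in the documents)**
- True duration T is exponential with median m, so λ = ln 2 / m and the true mean is 1/λ.
- Observation time C after onset is independent of T.

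**Direction.** If ongoing responses are entered at their last observed time, the mean estimates E[min(T, C)], which is below E[T] whenever some responses are ongoing. If they are dropped, it estimates E[T | T ≤ C], which keeps the shorter responses.

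**Size, fixed C = 10 months**
- Proportion ongoing: exp(−λC)
- Mean, ongoing entered as ended: (1 − exp(−λC)) / λ
- Median, ongoing entered as ended: min(m, C)
- Mean, completed only: 1/λ − C·exp(−λC) / (1 − exp(−λC))
- Median, completed only: −ln(1 − F/2) / λ, with F = 1 − exp(−λC)

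For m = 12: λ = 0.0578 and exp(−0.578) = 0.561. The mean with ongoing entered as ended is 0.439 / 0.0578 = 7.6. The completed-only mean is 17.3 − 10 × 0.561 / 0.439 = 4.5.

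| True median | True mean | Ongoing | Mean, entered as ended | Median, entered as ended | Mean, completed only | Median, completed only |
|---|---|---|---|---|---|---|
| 6 | 8.7 | 31% | 5.9 | 6.0 | 4.1 | 3.6 |
| 12 | 17.3 | 56% | 7.6 | 10.0 | 4.5 | 4.3 |
| 18 | 26.0 | 68% | 8.3 | 10.0 | 4.7 | 4.5 |
| 24 | 34.6 | 75% | 8.7 | 10.0 | 4.8 | 4.6 |

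As the true mean goes from 8.7 to 34.6 months, the mean with ongoing responses entered as ended moves only from 5.9 to 8.7.

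**Size, staggered follow-up.** These are 10,000 simulated trials per case with C uniform. Paired values are for 6 / 12 responders. Naive means ongoing responses are entered as ended.

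| C (months) | True median | Ongoing | Naive mean | Naive median | Kaplan-Meier median reached | Middle Kaplan-Meier median |
|---|---|---|---|---|---|---|
| 2–12 | 6 | 47% | 4.6 | 4.3 / 4.1 | 78% / 84% | 5.2 / 5.8 |
| 2–12 | 12 | 68% | 5.6 | 5.4 / 5.3 | 42% / 41% | not reached |
| 2–24 | 6 | 29% | 6.2 | 5.3 / 5.0 | 96% / 99% | 4.9 / 5.6 |
| 2–24 | 12 | 50% | 8.6 | 7.8 / 7.5 | 75% / 82% | 10.9 / 11.9 |

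The naive mean is below the true mean throughout, and under staggered follow-up the naive median is below the true median throughout. The naive columns are averages over simulated trials and the last column is a middle value, so small differences between them should not be read closely.

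**The case against.** **The plan does not say that ongoing responses are counted as ended.** A reader might infer this from the choice of statistics, but the text never says how such responses are handled, and its list of statistics is introduced as examples. This stands as a limit on the wording. It does not rescue the method: no censored method or censoring rule is given for duration of response, the same paragraph uses Kaplan-Meier for EFS and OS, and both simple ways of computing a mean understate it.

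**The bias is not universal.** This stands for the median. With a fixed cut-off longer than the true median, and ongoing responses kept in, the median is right: the table gives 6.0 for a true 6. It would be wrong to claim that every summary under this plan is biased.

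**The size is assumed.** This stands. A reader might also take 12 months as a hard limit, but Section 4.0 allows treatment beyond it, and longer follow-up shrinks the bias. The phone calls concern health status; by themselves they cannot establish relapse under Tables 9 and 10, which need counts, transfusion need or marrow blasts.

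**Nothing is decided on duration.** This stands. A reader might infer that the usefulness of a 15% ORR, and so the trial's conclusion, turns on it. The criteria for further investigation in Section 12.0 are ORR and toxicity, and duration is neither the primary endpoint nor one of the secondary endpoints in Section 10.0.

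**Kaplan-Meier offers little with 6 responders.** This stands in part. With a true median of 12 months and 10 months of observation, at least 3 events among 6 occur about 54% of the time, so the median is not reached in about 46% of trials. For short true durations the gain is small: with 2–24 months of follow-up, a true median of 6 and 6 responders, the middle Kaplan-Meier median is 4.9 and the naive average 5.3. But where most responses are ongoing, reporting the median as not reached is accurate, and a naive value near 5 months against a true 12 is not.

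**Conclusion.** The concern holds in a limited form. The plan puts a right-censored time under uncensored descriptive statistics, gives no censoring rule, and limits Kaplan-Meier to EFS and OS. If any response is ongoing at analysis, the mean is biased downward under either simple handling. The median is biased as well unless follow-up for all responders exceeds the true median and ongoing responses are retained.

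The direction for the mean needs only that some responses are ongoing, which the treatment plan makes likely. The size is illustrative. With exponential durations, a true median of 12 months and 10 months of observation, the mean is 7.6 or 4.5 months against 17.3, depending on the handling. The bias disappears if all responses have ended by analysis.

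The change should be made, but it concerns a descriptive summary only. ORR, the stopping rules and the listed endpoints are untouched.

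**What to change.** - **Method.** Take duration of response out of the descriptive-statistics sentence and add it to the Kaplan-Meier sentence.
- **Definition.** Separately for Part 1 and Part 2: time from first documented response to relapse or progression under Tables 9 and 10, or death.
- **Censoring.** Censor ongoing responses at the last assessment adequate for that type of response. This needs care. After Cycle 4 of Part 1, Sections 8.0 and 9.0 schedule blood counts before each course but no further routine marrow until Cycle 4 of Part 2, so a marrow-based response may have an early censoring date.
- **Start of HMA.** A Part 1 responder who moves to Part 2 under Section 4.0 has progressed, and that progression is the event. Censor at HMA start only if HMA begins without progression. State also how transplant is handled.
- **Reporting.** Give the Kaplan-Meier median with 95% CI, or state that it was not reached, together with the number of responses ongoing. Give landmark proportions only where follow-up supports them, such as 6 months. A 12-month proportion may not be estimable with about 8 to 11 months of observation after onset.

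**Cost.** A few sentences in the analysis plan and no new procedures. The downside is that with about 6 Part 1 responders at the 15% target, the estimate will be imprecise or the median not reached.

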Among patients with MF and advanced myeloid malignancies, side effects were predominantly GI. The most common AEs were diarrhea (81%), nausea (50%), fatigue (41%), vomiting (36%), anemia (26%), abdominal pain (23%), peripheral edema (24%), and constipation (20%). Grade 3/4 AEs were reported by 77% of patients. The most frequently occurring Grade 3/4 events in patients with MF were anemia (19%), thrombocytopenia (15%), fatigue (12%), and diarrhea (11%).

QTc Toxicities

CTI performed a post-hoc review of the phase 1-2 S*^BIO studies, SB1518-2007-001 and SB1518-2008-003, for potential cardiac toxicity, based upon a single case report of a QTc prolongation reported as a dose-limiting toxicity in the SB1518-2007-001 study. In these studies, ECGs were performed at baseline, periodically during the first 30 days of treatment, at termination, and as clinically indicated.

These studies have been completed. Clinical study reports are pending for Studies SB1518-2007-001 and -2008-003; thus, data are preliminary.

- Based on the identified DLT, CTI performed a full review of the patient profiles for all patients enrolled in these two studies. Review of these data identified the following observations:
- Nine patients across the studies had at least 1 reported QTc exceeding 500 ms, including the patient with the DLT. Of these 9 patients, 1 patient was receiving pacritinib at 150 mg per day, 1 at 450 mg per day, and the remaining 7 were receiving 400 mg per day. Baseline pre-pacritinib QTc intervals ranged from 441 to 491 ms. A majority (5) of the QTc prolongations were identified at the Day 29 time point, with the others identified on Days 1, 10, and 18.
 - At the time of the QTc events, 8 patients were on concomitant medications associated with QTc prolongation, including ondansetron (5 patients), levofloxacin (2 patients), venlafaxine (2 patients), and amiodarone, solifenacin, fluconazole, voriconazole, citalopram, cilostazol, and prochlorperazine in 1 patient each.
 - Pre-study cardiac history was also noted in 7 of the patients, including atrial fibrillation (3 patients), coronary artery disease (3 patients), myocardial infarction (3 patients), congestive heart failure (1 patient), heart murmur (2 patients), and syncope (2 patients).
- In addition to the DLT event, there were two QTc prolongations reported as non-serious AEs.

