- **Cardiac:** QTc prolongation has been reported in association with pacritinib therapy. A post-hoc review of the patients in the phase 1-2 Studies SB1518-2007-001 and SB1518-2008-003 identified 9 patients with at least one reported QTc exceeding 500 ms; all but one were treated at a pacritinib dose of ≥ 400 mg QD. Therapy was continued in most of these patients for extended periods of time after the observations of QTc prolongation. In addition, pre-study cardiac history was noted in 7 patients, and 8 patients were taking concomitant medications associated with QTc prolongation. Other cardiac TEAEs and ADRs were rare in all pacritinib-treated populations. Based on these observations, investigators are advised to exclude any patient with a baseline QTc > 450 ms and to perform routine ECG monitoring during treatment. For patients with identified changes in treatment-emergent ECG abnormalities or other cardiac events, study drug may be interrupted or the dose may be reduced per protocol.
- **Hepatic:** Animal studies suggest that pacritinib treatment may cause dose-related hepatotoxicity. There has been little evidence of hepatotoxicity in clinical trials to date. Significant increases in aminotransferases have been observed infrequently and have not been accompanied by concomitant increases in bilirubin. Most reported hepatic toxicities were seen in the myeloid population. No instances of hepatic dysfunction meeting Hy's Law criteria have been observed. Hepatic function (AST/SGPT, ALT/SGOT, alkaline phosphatase, and total bilirubin) will continue to be assessed at frequent intervals during treatment with pacritinib.
- **Renal:** Animal studies suggest that treatment may cause dose-related renal toxicity. To date, little impact on renal function has been observed in human clinical trials. Assessment of renal function (creatinine, BUN, sodium, potassium) will be undertaken frequently in patients participating in clinical trials of pacritinib.

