8.0 PATIENT EVALUATION

Pre-treatment

Results from tests performed as standard of care up to 28 days prior to study entry can be used for determining eligibility and establishing baseline measurements. Any clinically significant abnormal results (except for bone marrow aspiration) should be repeated within 48 hours of beginning therapy to establish a baseline.

- A complete history and physical exam including height, weight, and vital signs (blood pressure, heart rate, breathing rate, and temperature), disease documentation, and performance status (PS) should be performed 72 hours before initiation of study, and subsequently as indicated.
- Document significant baseline abnormalities and concomitant medications within 28 days of initiation of study.
- CBC, platelet count, creatinine, total bilirubin, AST and/or ALT, potassium and blood or urine pregnancy test (when indicated) should be performed 72 hours before initiation of study. Pregnancy testing will be conducted for any female that is of childbearing age that has not been surgically sterilized or without a menses for 12 consecutive months.
- Bone marrow aspirate and/or biopsy during the last 28 days preceding study initiation
- FLT3 and JAK2 mutational status (including FLT3 allelic ratio if mutation present). This can be performed on the pre-study bone marrow aspirate or from peripheral blood
- Cytogenetics will be obtained within 28 days prior to therapy, and should be repeated with all bone marrow assessments performed on study.
- EKG with documentation of QTc interval
- Echocardiogram or MUGA for evaluation of left ventricular ejection fraction
- Pretreatment correlative studies if patient signed for them during consent process.

During Treatment

- CBC, platelet count, creatinine, AST and/or ALT and total bilirubin weekly during first course of therapy, and prior to each course of therapy.
- Document adverse event assessment and concomitant medications at each clinic visit.
- EKG will be performed 4 hours post dosing on cycle 1 day 1 (+/- 1 hour) , on cycle 1 day 28 (+/- 5 days), cycle 4 day 28 (+/- 5 days), and as clinically indicated.
- Bone marrow aspiration on day 28 (+/- 5 days) of Cycle 1 and Cycle 4 of Part 1, and after

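### EKGs are scheduled on treatment for a named QTc risk, but no analysis counts patients above 500 ms, and in the earlier studies adverse-event reporting missed at least 6 of 9 such patients

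*Combined protocol and SAP*

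**What the plan says.** Section 6.0 (Observed Risks) states that "QTc prolongation has been reported in association with pacritinib therapy". It advises investigators to exclude patients with a baseline QTc above 450 ms and to monitor ECGs routinely, and Section 3.0 adopts the exclusion. Section 8.0 requires, before treatment, an "EKG with documentation of QTc interval". For the treatment period it says "EKG will be performed 4 hours post dosing on cycle 1 day 1", then again on day 28 of cycles 1 and 4, and when clinically indicated. Footnote 7 of the Section 9.0 calendar repeats these times.

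The Statistical Analysis Plan at the end of Section 12.0 has two statements on safety: "Toxicity type, severity and attribution will be summarized for each patient using frequency tables", and that "safety data of the patients will be summarized using descriptive statistics such as mean, standard deviation, median and range". It names no QTc threshold, no change from baseline and no other EKG analysis. The toxicity monitoring in Tables 11 and 14 counts drug-related non-hematological grade 3/4 events only.

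Section 13.0 enters into the database those grade 3 or 4 adverse events that are related and/or unexpected, together with protocol-specific data. A separate sentence restricts the case report form to unexpected events. Expectedness is judged against the Investigator Brochure.

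The background (Section 2.3, QTc Toxicities) describes a retrospective review of two earlier studies, SB1518-2007-001 and SB1518-2008-003: "Nine patients across the studies had at least 1 reported QTc exceeding 500 ms, including the patient with the DLT". It adds: "In addition to the DLT event, there were two QTc prolongations reported as non-serious AEs".

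**The concern.** Safety is part of the single objective in Section 1.0, and QTc is one of the few risks for which the protocol schedules a dedicated measurement. A harm that shows itself as a reading on a tracing is best counted from the tracings. The plan instead leaves it to whether someone reports the reading as an adverse event, grades it and attributes it. By the protocol's own account that route failed for most affected patients in the earlier studies, and they came to light only because one dose-limiting toxicity prompted a review of patient profiles.

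Attribution is a further weak point. Of the nine earlier patients, eight were taking drugs associated with QTc prolongation, so a similar case here could reasonably be called unrelated. It would then not count towards Table 11 or Table 14. The trial could follow its plan and report fewer QTc findings than its own EKGs contain.

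**Working it through.** **1. The documents' count of nine.** The background gives the doses as 1 patient at 150 mg, 1 at 450 mg and 7 at 400 mg: 1 + 1 + 7 = 9. Section 6.0 says that all but one were at 400 mg or more: 1 + 7 = 8 of 9. The two accounts agree.

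**2. How many reached adverse-event reporting.** The dose-limiting toxicity is one. The two non-serious events add at most two, and they need not have exceeded 500 ms.
- Reported: at most 1 + 2 = 3, at least 1.
- Not reported: at least 9 - 3 = 6 (6/9 = 67%), at most 9 - 1 = 8 (8/9 = 89%).

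The serious-event lists for the two studies contain no QTc prolongation, which is consistent with this.

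**3. The same gap as rates.** Treated patients number 74 + 54 = 128. Intervals are exact 95% (Clopper-Pearson).
- Above 500 ms: 9/128 = 7.0% (3.3% to 12.9%).
- Visible through adverse-event reports: at most 3/128 = 2.3% (0.5% to 6.7%).

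**4. Would the readings exist here?** Five of the nine prolongations were found at Day 29 and the others on Days 1, 10 and 18. The scheduled EKGs on day 1 and on day 28 (within 5 days) of cycle 1 cover the times at which most were found. What is missing is the analysis. There is one gap in recording: QTc documentation is spelled out only for the pre-treatment EKG and is merely implied afterwards.

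**5. What the recording rules let through.** Under the database rule, a grade 3/4 event is lost only if it is judged both unrelated and expected. The list of expected events in Section 13.0 does not include QTc prolongation, but the Investigator Brochure governs and is not part of these documents. For Tables 11 and 14 one judgement is enough, because an event called unrelated is not counted.

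**6. Does the toxicity monitor catch it?** The posterior rule with a Beta(0.3, 1.7) prior, a 15% limit and a 0.975 cut reproduces the Table 11 boundary exactly: 4/5, 5/10, 6/15, 7/20, 8/25, 10/30, 11/35. If every QTc event were counted as drug-related and occurred at 7.0%, those events alone would cross the boundary at any of the seven looks with probability 0.0009, about 0.1%. The monitor is no substitute for a separate count.

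**The case against.** The strongest reply has four parts.

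*The earlier experience may not carry over.* The earlier studies were graded under version 3.0 of the toxicity criteria, and their QTc review came afterwards. Here investigators are warned in advance, EKGs are timed to the dose, and version 4.0 applies. That could improve reporting, so it is not certain that this trial will under-report. It remains likely, because nothing in the plan replaces the route that failed before.

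*The event rate may be much lower.* The nine had baseline QTc values from 441 to 491 ms. This trial excludes values above 450 ms and atrial fibrillation of any grade, and it discourages QT-prolonging drugs. A reader might carry the 7.0% over and infer 40 x 9/128 = 2.8 affected patients and a 1 - (1 - 9/128)^40 = 95% chance of at least one. The documents do not support that. Only the patient at 441 ms is certain to have met the QTc limit. With one case in 128 the figures become 40/128 = 0.3 patients and 1 - (127/128)^40 = 27%. This objection stands against any forecast, though not against the reporting gap.

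*The recording rule is wider than it looks.* A reader might infer that an event judged unrelated simply vanishes from the database. The rule also admits unexpected events, and protocol-specific data may include EKG values. This too stands. The firm loss from an unrelated call is from the Table 11 and Table 14 counts.

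*The range would show an extreme value.* If the generic statistics are applied to QTc, the range does reveal a maximum above 500 ms. It does not show how many patients exceeded that value or how far they moved from screening.

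**Conclusion.** The concern holds as a likely under-count. For a named risk with scheduled measurements, the plan has no analysis of those measurements, and the documents' own evidence is that adverse-event reporting missed between 6 and 8 of 9 patients with QTc above 500 ms. The lower figure already gives the benefit of the doubt, because it assumes that both non-serious events belonged to the nine. It rests on the QTc Toxicities subsection as available; text that follows it was not available and could add detail.

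The size in this trial cannot be forecast. The 7.0% is illustrative, and the documents do not establish that QTc toxicity will be hidden altogether. The point deserves a change to the plan, but it does not put the primary efficacy result at risk.

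**What to change.** Add to the Statistical Analysis Plan in Section 12.0:

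- The number and percentage of patients, with an exact 95% confidence interval, who have any on-treatment QTc above 500 ms. This is the threshold that the documents themselves use. Include all scheduled and unscheduled EKGs, regardless of attribution or adverse-event reporting.
- A summary of each patient's maximum change in QTc from the screening EKG.
- Part 2 readings described separately, with the number of patients who had an EKG. Section 8.0 specifies a bone marrow examination for Part 2 but no EKG, so these readings may come mainly from patients tested for clinical reasons.

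In Sections 8.0 and 9.0, state that the QTc value is recorded from every on-treatment EKG. Before each look under Table 11 or Table 14, reconcile readings above 500 ms with the adverse-event record, so that attribution is decided explicitly. Further cut-offs, such as above 480 ms or an increase above 60 ms, are optional and do not come from the documents.

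The interval matters even if no reading is high: with 0 of 40 patients the exact upper limit is 1 - 0.025^(1/40) = 8.8%.

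The cost is a short addition to the plan, one table and a reconciliation step at each look. The reported QTc rate may look less favourable. No dose or clinical rule changes.
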